### 9.2.2 Study Period

The study period will start on the date AZD1222 vaccination began in each country. The first vaccinations started approximately 1 week after approval date, which was 30 December 2020 in the UK and 29 January 2021 in the EU. The study period duration will be 24 months in each data source or until latest data available at the time of start of data collection (data extraction), ie, this duration may include a few more months in the data sources where the lag time to obtain the data is shorter.

### 9.2.3 Follow-up and Time at Risk

[figure not shown]
Follow-up time will start on the date that all inclusion criteria are met and will end at the earliest of the occurrence of censoring conditions or the last data extraction/data availability as defined for each study design.

#### 9.2.3.1 Cohort Design: Follow-up

Follow-up will start on the index date and end on the earliest of the following possible follow-up termination dates:

- The end date of the study period.
- The subject's enrolment termination date in the health plan or system.
- The subject's date of death.
- For the specific evaluation of each AESI:
  - The date of the first diagnosis of a specific AESI recorded after the index date, during the study period. For composite outcomes, follow-up will be censored at the date of the first occurrence of any of the components.
  - For the evaluation of AESIs with **known risk windows** (ie, those for which the end of the risk window is other than 180 or 365 days), the date on which the defined risk window for the last dose ends (the last dose was dose 1 if only 1 dose was received and dose 2 if 2 or more doses were received).
    - For subjects who received 2 doses of AZD1222, or of an mRNA vaccine, and were not censored due to an AESI or other censoring criteria before the second dose, a second risk window will follow the second dose; and for concurrent unvaccinated comparators or historical comparator subjects, a corresponding second risk interval will also apply, mirroring the timing of the second risk interval for the matched vaccinee (Figure 4). As previously noted, the start and duration of the risk windows will be specific to each outcome, corresponding to the period when the biologic effect of a vaccine is hypothesised to increase the risk for the particular AESI (Section 9.1.2). If an AESI occurs during a gap between doses, this AESI will not be included as an event in the study, and as stated above, the follow-up will be censored at the time of the AESI.
    - This risk window applies to both the vaccinee and matched comparator subjects.

**Figure 4. Time at Risk for an AESI With a Known Risk Window in Subjects With 2 Doses of AZD1222**

AESI, adverse event of special interest.

- For the evaluation of AESIs with an **unknown risk window** (those with a risk window that ends at 180 or 365 days), follow-up will comprise all person-time after the index date and will extend 180 or 365 days (Table 3) after the last AZD1222 or mRNA vaccine dose (dose 1 if only 1 dose was received and dose 2 if 2 or more doses were received) for vaccinated subjects or the corresponding time for the unvaccinated and historical comparators.
- For the AZD1222 cohort:
  - 365 days after the second vaccine dose. This rationale is 2-fold. First, because we expect that most comparators will become vaccinated during the study period, this choice will reduce the anticipated mismatch of follow-up time duration between the exposed and comparator cohorts. Second, although the risk window for some AESIs is not defined, vaccine-associated adverse events are unlikely to manifest beyond 1 year. To include person-time in the risk window when a vaccine effect could not reasonably occur may attenuate risk estimates, if a true risk exists.
  - The date on which the subject received a dose of any COVID-19 vaccine other than AZD1222.
  - The date on which a subject receives a 3rd dose of any COVID-19 vaccine
- For the active comparator cohort:
  - 365 days after the second vaccine dose.
  - The date on which the subject received a dose of any COVID-19 vaccine other than Comirnaty or Spikevax.
  - The date on which a subject receives a 3rd dose of any COVID-19 vaccine
- For the concurrent unvaccinated cohort, the date on which the subject received a dose of AZD1222, at which time the subject switches from the comparator to the AZD1222 cohort.

- For the historical comparator cohort, 31 October 2019, an estimate of the date when SARS-CoV-2 started to circulate in Europe.

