## 8. RESEARCH QUESTION AND OBJECTIVES

The primary study objectives are as follows:

- 1 To describe the baseline characteristics (eg, demographics, medical history) of all subjects in the *matched population*
- 2 To describe, among subjects who receive a first dose of AZD1222 (ie, in the *all AZD1222 vaccinated first dose population*), the timing and type of second dose of any COVID-19 vaccine (AZD1222 or other) over the study period
- 3 To describe the incidence rates (IRs) of prespecified AESIs in subjects who received at least 1 dose of AZD1222 in the *matched population* and subjects who did not receive any vaccination against COVID-19 (concurrent unvaccinated comparators) in the *matched population*
- 4 To estimate the relative and absolute risk of prespecified AESIs in subjects who received at least 1 dose of AZD1222 compared with concurrent unvaccinated comparators in the matched populations, using a retrospective cohort design and an SCRI design

Secondary objectives are as follows:

- 1 To describe the baseline characteristics (eg, demographics, medical history) of all subjects in the matched population among the specific populations considered to have missing information (Section 9.2.1.2)
- 2 To describe, among subjects who receive a first dose of AZD1222, (ie, in the *all AZD1222 vaccinated first dose population*), the timing and type of second dose of any COVID-19 vaccine (AZD1222 or other) over the study period among the specific populations considered to have missing information
- 3 To describe the IRs of prespecified AESIs in subjects who received at least 1 dose of AZD1222 in the *matched population* and subjects who did not receive any vaccination against COVID-19 (concurrent unvaccinated comparators) in the *matched population*, among the specific populations considered to have missing information
- 4 To estimate the relative and absolute risk of prespecified AESIs in subjects who received at least 1 dose of AZD1222 compared with concurrent unvaccinated comparators in the matched populations, among the specific populations considered to have missing information, using a retrospective cohort design and an SCRI design

Exploratory objectives are as follows:

- 1 To describe the IRs of prespecified AESIs in subjects who received an mRNA vaccine against COVID-19 (either Comirnaty or Spikevax) (active comparators) and in subjects

- from the pre-pandemic period (2017-2018) (historical comparators) in the matched population

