**Figure 3 Eligibility Criteria and Index Date Definition**

AESI, adverse event of special interest; FU, follow-up; SARS-CoV-2, severe acute respiratory syndrome coronavirus 2.

Subjects in the concurrent unvaccinated cohort will be allowed to enter any of the AZD1222 or active comparator cohorts if they later fulfil specific cohort entry criteria. Subjects in the active comparator cohort will not be allowed to enter the AZD1222 cohort, and vice versa. Subjects in the historical comparators cohort will be allowed to enter the any of the other cohorts if they later fulfil specific cohort entry criteria.

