**Figure 6 Summary of Covariate Ascertainment in Cohort Analyses**

a Earliest end date of study period, enrolment termination date, death, vaccination with any COVID-19 vaccine other than the vaccine granting access to the cohort, also for each specific AESI: date of the AESI, end of risk window for that specific AESI.

Note that information on inclusion, exclusion, and covariate assessment windows will all be available before the index date in each data source, except when an alternative look-back-specific risk window is specified. For comedications and healthcare utilisation, this time window will be 183 days before the index date, except if a different time window is specified for specific medications or healthcare utilisation measures.

AESI, adverse event of special interest; COVID-19, coronavirus disease 2019.

Source: Original design diagram template can be found at [www.repeatinitiative.org/projects.html](http://www.repeatinitiative.org/projects.html).

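### Section 9.2.3.1 ends follow-up of unvaccinated comparators only at a dose of AZD1222, which conflicts with the Figure 6 footnote and the primary objectives

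*Protocol*

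**What the plan says.** Section 9.2.3.1 of the protocol opens its list with "Follow-up will start on the index date and end on the earliest of the following possible follow-up termination dates". The items for all cohorts are end of study period, disenrolment, death, the AESI itself and the end of the risk window. None of them is a COVID-19 vaccination.

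Vaccination appears only in the cohort-specific items after Figure 4:

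- AZD1222 cohort: "The date on which the subject received a dose of any COVID-19 vaccine other than AZD1222", or any third dose.
- Active comparator cohort: "The date on which the subject received a dose of any COVID-19 vaccine other than Comirnaty or Spikevax", or any third dose.
- Concurrent unvaccinated cohort: "For the concurrent unvaccinated cohort, the date on which the subject received a dose of AZD1222, at which time the subject switches". No other vaccine is named.

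Other places describe the unvaccinated cohort more broadly. Primary objective 3 in Section 8 refers to "subjects who did not receive any vaccination against COVID-19 (concurrent unvaccinated comparators", and Section 9.1 describes the same group as people still without any COVID-19 vaccine. Footnote a of Figure 6 (Section 9.3.3) lists, among the events that end follow-up, "vaccination with any COVID-19 vaccine other than the vaccine granting access to the cohort". The entry criterion in Section 9.2.1.1.3 also requires no COVID-19 vaccine of any kind, but it governs eligibility at matching and not what happens afterwards.

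**The concern.** A programmer working from Section 9.2.3.1 alone would keep a comparator who receives Comirnaty or Spikevax in the unvaccinated arm until some other end date applied. Primary objectives 3 and 4 would then no longer compare AZD1222 with no vaccination. The reference arm would be a mixture of unvaccinated and mRNA-vaccinated time.

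If an mRNA vaccine raises the rate of an AESI, the mixture inflates the reference rate and pulls the IRR or HR down. In a safety study that can hide a real risk. If vaccination lowers the rate, as is plausible for COVID-19-related outcomes, the estimate moves up instead.

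The mirrored second risk window is the more exposed of the two. It opens when the matched vaccinee receives dose 2, which is 28 to 84 days after dose 1 on the schedule in Section 7, so a comparator has had time to be vaccinated before it starts. The planned sensitivity analysis that censors both members of a pair (Section 9.7.10) would not reveal the problem, because it acts only when one member is censored under the rules as stated.

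**Working it through.** **1. The passages side by side.**

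| Place | What ends, or excludes from, unvaccinated status |
|---|---|
| Section 9.2.3.1, bullet after Figure 4 | AZD1222 only |
| Figure 6, footnote a | Any COVID-19 vaccine other than the one giving entry; this cohort is entered without a vaccine, so any vaccine |
| Section 8, primary objective 3 | Any COVID-19 vaccination |
| Section 9.1 | Any COVID-19 vaccine |
| Section 9.3.2 | Supports the cohort risk windows on the ground that comparator time is free of time at risk, unrecorded vaccinations apart |

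The Section 9.2.3.1 bullet is the odd one out. Under it, even recorded mRNA vaccinations would stay in comparator time.

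**2. The plan's own figure for this comparison.** Section 9.5 states a 75% probability that the upper limit for GBS falls below 3.0, with 5 million vaccinated, 2 events per 100,000 person-years, 84 days at risk, person-time 3:1 and a true IRR of 1.

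- Vaccinated events: a = 5,000,000 × 84/365.25 × 2/100,000 = 23.0
- Comparator events: b = 23.0/3 = 7.67
- SE = √(1/23.0 + 1/7.67) = 0.417
- P = Φ(ln 3/0.417 − 1.96) = Φ(0.67) = 0.75

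This reproduces. The point below concerns bias and does not show the precision tables to be wrong.

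**3. Size if the rule were applied literally.** Let λ be the truly unvaccinated rate, m the share of comparator person-time after a non-AZD1222 vaccine, and R the rate ratio of that time to truly unvaccinated time. The comparator rate becomes (1−m)λ + mRλ = λ[1 + m(R−1)], so

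observed IRR = true IRR / [1 + m(R−1)].

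The formula is exact for a ratio of rates. For a Cox HR it is approximate, since m changes over follow-up. The protocol gives neither m nor R, so all values below are assumptions. For a true IRR of 2.0:

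| | m = 0.10 | m = 0.25 | m = 0.50 |
|---|---|---|---|
| R = 1.5 | 1.90 | 1.78 | 1.60 |
| R = 2 | 1.82 | 1.60 | 1.33 |
| R = 3 | 1.67 | 1.33 | 1.00 |

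A true IRR of 1.0 with R = 2 becomes 0.91, 0.80 and 0.67. In the other direction, m = 0.25 and R = 0.5 gives 2.0/(1 − 0.125) = 2.29. Censoring at any COVID-19 vaccine sets m = 0 and removes the distortion.

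**4. Is the literal rule likely to be in use?**

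- Section 9.1.1 reports median comparator follow-up below 2 months in every data source.
- Crude AZD1222 uptake from Table 4 (Interim Report 2 count over enrolled population): CPRD 4,301,194/13.4 million = 32%; VID 530,226/5 million = 11%; SIDIAP 614,472/5.8 million = 11%; ARS Toscana 343,478/3.6 million = 10%; PHARMO 175,149/3.5 million = 5%.
- Section 9.5 reports vaccinated-to-unvaccinated person-time of 2:1 in Interim Report 1 despite 1:5 matching. If all five matches were found, mean comparator follow-up was (1/2)/5 = 0.10 of the vaccinees'.

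Uptake of 5% to 32% would not readily cut comparator follow-up this short if AZD1222 were the only vaccine that ended it. The uptake figures are not age-specific, so this is indicative only.

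**The case against.** The strongest reply is that the protocol already contains the right rule. The Figure 6 footnote covers any vaccine, and Sections 8 and 9.1 agree with it. The interim data fit that rule, and Section 9.2.3.1 itself expects most comparators to become vaccinated and so to have shorter follow-up than vaccinees. On this view the bullet is loose wording and no estimate is affected. Much of this stands: it shows what was probably intended and perhaps already programmed. It does not cure the bullet, which sits in the section that defines follow-up and spells out broader rules for the two neighbouring cohorts.

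Three stronger readings might be inferred, and the documents do not support them:

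- *Post-mRNA time is being counted as unvaccinated.* The text shows a contradiction, not what the code does, and the follow-up figures point the other way.
- *m must be large because AZD1222 was no longer given by Interim Report 2.* Comparators take the index date of their matched vaccinee (Section 9.2.1.1.3), so they enter while AZD1222 is in use. For the 180- and 365-day windows, Sections 9.1.1 and 9.9.1 already call concurrent follow-up too short.
- *The text with Figure 3 contradicts the bullet.* It says "Subjects in the concurrent unvaccinated cohort will be allowed to enter any of the AZD1222 or active comparator cohorts" if they later qualify, but it sets no end date for the cohort they leave. It is silent on the matter. Appearing in two independently matched sets is not in itself an error.

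**Conclusion.** The bullet is wrong as written. It states a narrower end of follow-up than the Figure 6 footnote, and it is incompatible with the comparator defined in Sections 8 and 9.1. Because it defines the reference arm of primary objectives 3 and 4, it should not be left to interpretation.

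The size is conditional. If the bullet were followed, the IRR would be multiplied by 1/(1+m(R−1)): 2.0 would become 1.6 at m = 0.25 and R = 2, with little change if m is small or R is close to 1, and a shift upwards if R is below 1. Both inputs are assumptions. Actual bias in any reported or planned estimate is not shown.

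**What to change.** Reword the bullet in Section 9.2.3.1 along these lines: *for the concurrent unvaccinated cohort, the date of the first dose of any COVID-19 vaccine, after which the subject may enter the AZD1222 or the active comparator cohort if eligible.* State that the same rule applies to the mirrored second risk window, so that a comparator vaccinated before that window opens contributes nothing to it. Then confirm that the analysis code does this, and record the result.

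The cost is one sentence, a cross-reference and a code check, with the final analysis still to come. If the code already censors at any vaccine, no result changes. If it does not, comparator person-time will fall, any interim comparisons made under the narrow rule need rerunning, and the 3:1 person-time assumption behind Table 5 should be looked at again.

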### 9.2.3.2 SCRI Design: Follow-up and Time at Risk

The SCRI will be used for most of the AESI with known risk windows as per [Table 3](#). The SCRI evaluates occurrence of a particular AESI during a “risk interval” (exposed -person time) and a subsequent “control interval” (unexposed person-time) following vaccination with AZD1222 ([Figure 1](#)). Proposed outcome-specific risk intervals for the AESIs appear in [Section 9.3.2](#). Control intervals, which by design occur following the risk intervals, will have the same duration as the risk interval, except under the special circumstances explained below.

[Figure 1](#) illustrates this arrangement for a risk window that starts 1 day after vaccination and continues for 42 days. After a 7-day washout period, the control interval begins and ends after 42 days as well. It is important to note that in contrast to the cohort design, the occurrence of the outcome is not a censoring event for SCRI evaluation; the full duration of the risk interval and control intervals factors into the analysis. For subjects who receive a second dose, corresponding risk and control intervals follow the second dose as well.

In general, if the AESI occurs after dose 1 but before dose 2, the SCRI analysis includes only the risk and control intervals following dose 1. Similarly, if the AESI occurs after dose 2, the SCRI analysis includes only the risk and control intervals following dose 2.

The scenario depicted in [Figure 1](#) may be complicated if a subject receives a second vaccine dose before the control interval for the first dose has fully elapsed. In this situation, the first control period will be censored at the time of the second dose. Death of a subject during the control interval will also serve as a censoring event.

If a subject receives a second dose before the risk interval for dose 1 has completed, the risk periods will be concatenated and extended for the duration of the risk interval following the second dose. In this scenario, the SCRI analysis will include the -person time in the concatenated risk intervals and the control period following dose 2.

Details about AESI-specific risk intervals and washout periods will be specified in the SAP.

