## 7. RATIONALE AND BACKGROUND

The novel coronavirus SARS-CoV-2 (severe acute respiratory syndrome coronavirus 2), the cause of coronavirus disease 2019 (COVID-19), has led to a global pandemic. AZD1222 (called Vaxzevria® in Europe) is a vaccine that was developed to prevent COVID-19.

Coronaviruses are enveloped viruses with positive-sense single-stranded RNA genomes. The spike glycoprotein is a coronavirus surface protein involved in receptor binding and mediating

virus entry into host cells during infection (Li 2016). AZD1222 is a recombinant replication-defective chimpanzee adenovirus expressing the SARS-CoV-2 spike glycoprotein. Development of AZD1222 was initiated by the University of Oxford with subsequent transfer of development activities to the Sponsor.

On 30 December 2020, the UK Medicines and Healthcare products Regulatory Agency (MHRA) provided authorisation for emergency supply of AZD1222, and on 29 January 2021, the European Commission granted conditional marketing authorisation for the vaccine. Now known as COVID-19 Vaccine AstraZeneca, the vaccine in both jurisdictions is indicated for active immunisation to prevent COVID-19 caused by SARS-CoV-2, in individuals aged 18 years and older. The vaccination course consists of 2 separate intramuscular injections. The second dose should be administered between 4 and 12 weeks (28 to 84 days) after the first dose. Since May 2022, a booster dose may be given at least 3 months after the second dose. A booster dose of AZD1222 can also be given to adults who have had 2 doses of an authorised mRNA COVID-19 vaccine but is beyond the scope of this study. At the national level, public health bodies may issue official recommendations, taking into account emerging effectiveness data and the limited safety data.

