**Table 3 Adverse Events of Special Interest and Other Safety Concerns**

Adverse event	Suitable for SCRI analysis according to ACCESS protocol template a	Risk interval after index date (days)	Clean look-back interval (days) k
Vaccine-associated enhanced disease, including vaccine-associated enhanced respiratory disease, including ARDS	No	14-365 b	365
Multisystem inflammatory syndrome in adults/children	Yes	1-42 c	365 c
Sudden death	No	0-6 b	Not applicable
Autoimmune thyroiditis	No d	1-180 e	365
Anosmia, ageusia	No f	1-365 e	365
Anaphylaxis	Yes	0-2 c	180 c

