Second, the precision for the results comparing **AZD1222-vaccinated subjects with active comparators and historical comparators** was estimated. The estimation of the precision of the results assumed a 1:1 ratio for the person-time of AZD1222-vaccinated subjects to active comparators and to historical controls (Kaura et al 2022). For one of the rarest anticipated events, GBS, assuming a background rate of 2 events per 100,000 person-years, 84 days at risk (42 days per dose), and a study size of 5 million vaccinated subjects, it was anticipated that there was a 96% probability that the upper bound of the 95% CI around the observed IRR would be below 3.0 (Table 6).

The number of AZD1222 vaccinees and data sources for the comparison of AZD1222 vaccinees with active and historical comparators is considered acceptable for the purpose of

interpreting findings as continuous measures that are estimated with varying degrees of precision. Assuming 1:1 ratio of matching will be achieved with the 5.8 million AZD1222 vaccinated subjects, no additional data sources are considered necessary.

**Table 6 Probability That the Upper 95% Confidence Limit of the Observed IRR Will Be Below 1.5, 2, 2.5, and 3 for Various Study Sizes of Vaccinated Subjects, Assuming That the True RR is 1 and the Ratio of Vaccinated Subjects to Active Comparators Person-time and to Historical Comparators Person-time is 1 to 1**

Adverse event (duration of risk interval after each dose)	Estimated background rate per 100,000 PY	People vaccinated	Upper confidence limit of IRR			
			1.5	2.0	2.5	3.0
Anaphylaxis (VAC4EU 2021, Willame et al 2021)	6	1,000,000	0.05	0.07	0.09	0.12
(3 days)	6	2,000,000	0.06	0.10	0.15	0.19
	6	3,000,000	0.07	0.13	0.20	0.27
	6	4,000,000	0.08	0.16	0.25	0.34
	6	5,000,000	0.09	0.19	0.30	0.41
GBS (VAC4EU 2021, Willame et al 2021)	2	1,000,000	0.09	0.18	0.28	0.38
(42 days)	2	2,000,000	0.14	0.32	0.50	0.65
	2	3,000,000	0.19	0.44	0.67	0.82
	2	4,000,000	0.23	0.56	0.79	0.92
	2	5,000,000	0.28	0.65	0.87	0.96
Bell's palsy (Morales et al 2013) (42 days)	38	1,000,000	0.76	1.00	1.00	1.00
VTE a (Heit 2015) (42 days)	100	1,000,000	0.99	1.00	1.00	1.00

a This adverse event is a constituent of the composite AESI “thrombosis.”

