Estimated 4-week incidence among vaccinated individuals	Estimated 4-week incidence among concurrent unvaccinated individuals	People vaccinated	Upper confidence limit of ARD (per 100,000)			
			1.5	2.0	2.5	3
1 per 100,000	0	1,000,000	0.35	0.89	> 0.99	> 0.99
		2,000,000	0.61	0.99	> 0.99	> 0.99
		3,000,000	0.78	> 0.99	> 0.99	> 0.99
		4,000,000	0.89	> 0.99	> 0.99	> 0.99
		5,000,000	0.94	1.00	1.00	1.00
			Upper confidence limit of ARD (per 250,000)			
			1.5	2.0	2.5	3
1 per 250,000	0	1,000,000	0.17	0.52	0.85	0.98
		2,000,000	0.29	0.81	0.99	> 0.99
		3,000,000	0.41	0.93	> 0.99	> 0.99
		4,000,000	0.52	0.98	> 0.99	> 0.99
		5,000,000	0.61	0.99	> 0.99	> 0.99

Note: The actual incidence of TTS is not known; estimates here are based on reporting rates among vaccinated subjects (WHO 2021). The actual background incidence of TTS is also unknown. Calculations presented here assume a 1-to-1 ratio of vaccinated to unvaccinated subjects and follow the methods described in Rothman and Greenland (2018).

[figure not shown]
ARD, absolute risk difference; TTS, thrombosis with thrombocytopenia syndrome; WHO, World Health Organization.

Finally, the study size was estimated for the SCRI study component. The methods described by Musonda et al (2006) were used. These methods follow a traditional power and statistical

significance approach and do not currently allow a precision approach. The 2 parameters of most interest and specific to the SCRI design are the proportion of the observation period in the exposed state (ie, 50% in this study) and the relative incidence of events during the observation period in the exposed state compared with the incidence of events during the observation period in the unexposed state (ie, IRR). For this estimation, we assumed several IRR scenarios of 1.5, 2, 3 and 4. The study size estimation is not based on independent subjects but rather on the occurrences of the event of interest, which may happen more than once in the same subject. The SCRI includes only subjects that experienced the event of interest at least once.

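### Tying the SCRI control interval to the risk interval leaves anaphylaxis 3 control days per dose; a longer control interval would recover precision at almost no cost

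*Protocol*

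**What the plan says.** Section 9.2.3.2 sets the length: "Control intervals, which by design occur following the risk intervals, will have the same duration as the risk interval", with exceptions set out in the rest of that section. Two of those exceptions concern the second dose. If it falls inside the first control interval, "In this situation, the first control period will be censored at the time of the second dose". If it falls inside the first risk interval, "the risk periods will be concatenated and extended for the duration of the risk interval following the second dose". Death also censors the control interval. None of these lengthens a control interval. The section leaves risk intervals and washouts to the SAP, but it states the control length itself.

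Table 3 reads "Anaphylaxis Yes 0-2" for anaphylaxis, SCRI suitability and risk interval. The study-size text in 9.5 carries the equal-length rule into the power calculation, taking as a key parameter "the proportion of the observation period in the exposed state (ie, 50% in this study".

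Section 9.7 has each database analysed separately, with pooling if appropriate. Section 9.7.8 uses conditional Poisson regression for the SCRI.

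On timing, section 7 says: "The second dose should be administered between 4 and 12 weeks (28 to 84 days) after the first dose".

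**The concern.** In an SCRI the control interval supplies the denominator of the rate ratio. For a 42-day risk window an equal control interval is ample. For a 3-day window it discards most of the usable follow-up after the washout, although those days are already in the data.

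Anaphylaxis is one of the RMP safety concerns listed in section 7. A database with no control event has no finite point estimate and no upper limit for its IRR, and it adds little or nothing to an inverse-variance pooling of database estimates. Nothing in the method requires equal lengths: a person-time offset handles unequal ones, and the censoring rules in 9.2.3.2 already produce them.

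**Working it through.** **Inputs.**
- Background rate: 6 per 100,000 person-years (Tables 5 and 6).
- Risk window: days 0-2, 3 days per dose, 6 days per person over two doses (Table 3; notes to Tables 5 and 6).
- Vaccinees in Interim Report 2 (Table 4): CPRD 4,301,194; SIDIAP 614,472; VID 530,226; ARS Toscana 343,478; PHARMO 175,149; total 5,964,519.
- Assumption: everyone received two doses. This is an upper bound; with one dose each, expected counts halve.
- Assumption: a 7-day washout, borrowed from the 42-day example in Figure 1, because the SAP is to set the washout for each AESI.

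**Reproducing the plan's figures.** Table 6 gives 0.41 for the probability that the upper limit is below 3.0 with 5 million vaccinees at 1:1 person-time. Expected events per arm are 5,000,000 × 6/365.25 × 0.00006 = 4.93. Then Φ(ln 3 / √(2/4.93) − 1.96) = 0.41, which agrees.

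**Expected control events.** E = N × (control days × 2)/365.25 × 0.00006, and P(none) = exp(−E). With the 7-day washout the equal-length control is days 10-12 (3 days). The alternative, days 10-27, is 18 days, so E is six times larger.

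| Database | E, 3 days | P(none) | E, 18 days | P(none) |
|---|---|---|---|---|
| CPRD | 4.24 | 1.4% | 25.4 | <0.1% |
| SIDIAP | 0.61 | 55% | 3.6 | 3% |
| VID | 0.52 | 59% | 3.1 | 4% |
| ARS Toscana | 0.34 | 71% | 2.0 | 13% |
| PHARMO | 0.17 | 84% | 1.0 | 35% |
| All five | 5.88 | 0.3% | 35.3 | <0.1% |

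**Finite, non-zero IRR.** This needs an event in both intervals: (1 − exp(−E_control)) × (1 − exp(−E_risk)), where E_risk = IRR × E(3 days).

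| Database | IRR 1: 3 → 18 days | IRR 4: 3 → 18 days |
|---|---|---|
| SIDIAP | 21% → 44% | 41% → 89% |
| VID | 17% → 39% | 36% → 84% |
| ARS Toscana | 8% → 25% | 21% → 65% |
| PHARMO | 2% → 10% | 8% → 32% |

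**Precision, all five combined.** SE(log IRR) = √(1/E_risk + 1/E_control).
- IRR 1: √(1/5.88 + 1/5.88) = 0.58; √(1/5.88 + 1/35.3) = 0.45.
- IRR 4: √(1/23.5 + 1/5.88) = 0.46; √(1/23.5 + 1/35.3) = 0.27.

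**Power at IRR 3, two-sided 5%.** I used the signed-root likelihood-ratio formula for self-controlled designs. It gives 81%, 81% and 91% for three scenarios in 9.5 (IRR 1.5 with 200 events, IRR 2 with 70, IRR 3 with 40), in line with the text. For the fourth (IRR 4, 20 events) it gives 82%, where 9.5 says more than 90%; that is a separate matter and is not used here.
- Equal length: 5.88 × (3 + 1) = 23.5 events, exposed share 3/6 = 50%, power 71%.
- Days 10-27: 5.88 × (3 + 6) = 52.9 events, exposed share 3/21 = 14%, power 92%.
- One dose only: 41% and 68%.

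**The case against.** Much of the case on the other side stands.

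- **The study is not left without an estimate.** A reader might infer that the anaphylaxis SCRI cannot be estimated at all. The figures do not support that: CPRD holds 72% of vaccinees (4,301,194 / 5,964,519) and almost always has a control event, as do the combined data. Section 9.7.11 leaves the pooling method open, and a one-stage conditional likelihood could still use a database that has risk events but no control events.
- **The risk side is sparse too.** Control length cannot change the number of risk events. At a true IRR of 1 the four small databases would still lack a finite, non-zero IRR 56% to 90% of the time after the change.
- **Low precision is disclosed, and the SCRI is complementary.** Section 9.9.2 names anaphylaxis as a very rare endpoint, 9.1.2 makes the cohort design primary, and anaphylaxis has its own cohort measures. This limits the weight of the point but gives no reason to discard usable control time.
- **Other AESIs.** A reader might extend the point to convulsions, acute kidney and liver injury, myocardial infarction and ARDS. The document does not support that: its precision tables give no background rates for these events, so sparsity is not shown. For the 28-day AESIs, 42 control days after a 7-day washout would be days 36-77, inside the 28-to-84-day second-dose span, so truncation would take back part of the gain. Longer control time also spans more change in infection risk, which the SCRI does not remove by design.
- **Time between risk and control days.** For anaphylaxis this cost is small: days 10-27 lie closer to vaccination than the days 50-91 that the plan accepts for 42-day AESIs.

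**Conclusion.** The point holds for anaphylaxis as an avoidable loss of precision. Equal-length intervals are valid, so this is not an error or a source of bias. In four of five databases the rule leaves fewer than one expected control event and a 55% to 84% chance of no finite database-level IRR. In CPRD and overall, the IRR remains estimable but is less precise than the data allow: the variance of log IRR at IRR 1 could fall by about 42% (1 − (1 + 1/6)/2).

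The result rests on the protocol's rate of 6 per 100,000 person-years, two doses for all, and an illustrative 7-day washout. SIDIAP would reach one expected control event at about 9.9 per 100,000, PHARMO only at about 34.8. The standard errors are large-sample approximations on few events. I would treat it as a cheap, worthwhile improvement.

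**What to change.** In 9.2.3.2, for anaphylaxis only:
- Run the control interval from the end of the SAP-specified washout to a fixed later day before the earliest on-schedule second dose (for example days 10-27 with a 7-day washout).
- Truncate it at the next COVID-19 vaccine dose.
- Use log(person-days) as the offset in the conditional Poisson model.
- Keep the equal-length interval as a sensitivity analysis.

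In 9.5, note that the 50% exposed share does not apply to anaphylaxis.

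The cost is a sentence or two in the protocol and SAP and one programming parameter, with no new data. The downside is slightly more calendar time between risk and control days.
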